6.0 STUDY PROCEDURES

6.1 VT or PVC Ablation will be Performed According to Standard-of-Care Clinical Practice

Duration (mins)	STANDARD CLINICAL PROTOCOL	RESEARCH PROTOCOL	
		EP team	Anesthesia team
---	Pre-procedure holding room		Pre-drug muscle strength (grip and NIF)
60-140*	Clinical ablation procedure completed		
5	Post-ablation EPS & inducibility	Pre-drug EPS & inducibility	NIF, tidal volume, minute ventilation, ABG
5	Post-ablation ICE survey	LVERP & conduction time testing	
5	Post-ablation hemodynamics	Pre-drug hemodynamics	
3		Study drug given	
10		PK/PD blood sampling with measurement of ECG intervals and Fick cardiac output	NIF, tidal volume, minute ventilation, ABG
5		LV ERP & conduction time testing	
5		Post-drug hemodynamics	
2		Post-drug inducibility testing	
5			
---	Procedure completed		2-hour post-drug muscle strength (grip and NIF) and ABG
5	Post-procedure care unit		

Table 2. List of peri-procedural clinical and research activities. NIF: negative inspiratory force; ICE: intracardiac echocardiogram; LVERP: left ventricular effective refractory period; PK/PD: pharmacokinetics/pharmacodynamics.

This is a description of the clinical activities for VT or PVC ablation. **Table 2** provides an overview of the timeline for clinical and research activities. VUMC is a high-volume PVC and VT ablation center that in 2018 performed greater than 250 VT ablations. [name] directs the VT ablation research program at VUMC and has been a pioneer in the field. He, along with other international experts, authored the 2019 Heart Rhythm Society's expert consensus statement on catheter ablation for VT.⁵⁴ VT or PVC ablation will be performed according to our standard clinical practice. When feasible, amiodarone is held for 48 hours prior to ablation. Other oral AADs will be held 24 to 48 hours prior to the procedure and continuous I.V. AADs will be held 4 to 6 hours prior to the beginning of the procedure. Sedation during PVC or VT ablation and study protocol will be per usual care and remain at the attending anesthesiologist's discretion. Typically, PVC or VT ablations are done under monitored anesthesia care (MAC) with varying levels of sedation from moderate to deep sedation, although general anesthesia with or without a secured airway can occur. Propofol and dexmedetomidine infusions are typically used to achieve the desired level of anesthesia. The procedure will be performed with sterile preparation. The left ventricle will be accessed via either retrograde aortic or trans-septal access. Sheaths are placed in the femoral veins and artery for central vascular access. Hemodynamics are monitored with a radial or femoral arterial line, and a PA catheter. Standard EP catheters include: 1) a quadripolar catheter placed in the right ventricle, 2) a multipolar mapping array, and 3) an irrigated-tip radiofrequency ablation catheter. An intracardiac echocardiogram (ICE) catheter is also placed. A pre-ablation survey with an intracardiac echocardiogram (ICE) is performed to inspect the heart for baseline abnormalities (e.g. thrombus, pericardial effusion). A 3D mapping system is used to create an electroanatomic voltage map where low voltage areas (bipolar electrograms <1.5 mV) identify regions of fibrosis/scar to help localize the potential VT substrate. An EP study is performed, which includes programmed ventricular stimulation to induce VT. The programmed ventricular stimulation protocol is pacing at a fixed rate for 8 beats at a cycle length of 400-600 ms followed by early extrastimuli. In most cases, the clinical VT, which resembles spontaneous VT recorded by an ICD or on ECG, can be induced. Non-clinical ventricular arrhythmias are also often encountered which are usually monomorphic VTs that differ from the spontaneously observed VT (typically having a faster rate than the clinical VT) or polymorphic VT. The clinical VT and nonclinical monomorphic VTs that have a cycle length slower or only 20 ms shorter than clinical VT are targeted for ablation starting in low voltage areas. The reentry circuit may be identified by mapping during VT (activation mapping). More frequently ablation targets are identified during sinus rhythm as areas in the scar where pacing replicates the VT morphology (pace mapping), or electrograms have characteristics of abnormal conduction consistent with reentry substrate. When it is suspected that ablation has eliminated the targeted VTs, programmed ventricular stimulation is repeated. If any sustained monomorphic VTs are induced, additional ablation may be performed if there are additional regions that can be identified for those VTs. Acute procedural success is defined as 1) absence of any inducible sustained monomorphic VT, or 2) modification of the arrhythmia substrate if the clinical VT is no longer inducible, but other VTs are induced. Acute procedural failure is defined as continued inducibility of the clinical VT. Following completion of ablation, post-ablation hemodynamics are recorded, and an ICE survey is performed. For stable patients undergoing elective VT ablation, such as our study population, post-anesthesia recovery is performed in the EP Lab and the patient leaves awake, extubated, and hemodynamically stable.

6.2 List of Encounters Detailing the Clinical and Research Activities

Encounter 1: Enrollment and Informed Consent

- Performed by the study team in the Vanderbilt Arrhythmia Clinic or Vanderbilt University Hospital.

Encounter 2: Time of Ablation

- The participant will arrive the morning of ablation to the EP pre-op holding room and undergo standard preparations for ablation according to the clinical protocols (e.g. labs, vitals, exam, procedural consent).
- The participant will undergo baseline muscle (grip) and respiratory (NIF) strength testing in the pre-op area.
- The participant is then transported to the operating room (EP lab) where standard of care ablation is performed under the direction of the clinical team. See section 6.1 for full details.
- Research activities will begin after completion of the ablation portion of the ablation procedure. Research activities occur concurrently with clinical activities and are performed by a dedicated physician and nurse team to avoid extending overall case time.
- The clinical post-ablation EP study with programmed ventricular stimulation will serve as the baseline (pre-dantrolene) assessment of cardiac electrophysiology parameters (conduction and refractoriness) and ventricular arrhythmia inducibility. Data analyses are performed offline following the case to avoid adding procedural time. See sections 6.3 to 6.6 for full details.
- Hemodynamic monitoring is routinely performed during ablation with an arterial line and pulmonary artery (PA) catheter (aka. Swann-Ganz Catheter). See sections 6.7 to 6.10 for full details. The pre-dantrolene arterial blood pressure mean right atrial, PA systolic, PA diastolic, mean PA pressure, and pulmonary artery wedge pressures will be recorded.
- Blood samples will also be drawn for calculation of a Fick cardiac output and for the pharmacokinetic (PK)/pharmacodynamic (PD) analysis. See section 6.12 for full details of the PK/PD analysis. A 2 mL sample from the femoral venous, arterial, and distal PA catheter will be collected.
- I.V. dantrolene will be administered over 3 minutes. Peak drug levels occur rapidly allowing the data collection protocol to proceed without delay.
- The post-dantrolene hemodynamics will be recorded.
- The post-dantrolene EP study with programmed ventricular stimulation will be repeated.
- A 2 mL sample from the femoral venous, arterial, and distal PA catheter will be collected at 5, 10, 15, and 20 minutes post-dantrolene. The total amount of blood collected during the ablation is 30 mL.
- Respiratory mechanics (tidal volume, rate, minute ventilation) and an arterial blood gas (ABG) will be measured at 0, 10, and 20 minutes, and need for additional respiratory support will be assessed continuously as is standard care (see Section 6.13).
- The clinical and research activities will be complete, and the participant will leave the operating room awake, extubated, and hemodynamically stable.
- The participant will undergo baseline muscle (grip) and respiratory (NIF) strength testing in the post-op recovery area and an ABG will be measured 120 minutes after study drug was initiated

Encounter 3: Post-ablation Day 0-2.

- Following ablation, the participant will be returned to the EP holding room. It is clinical standard-of-care for patients to remain in the hospital at least overnight for monitoring. They will be under nursing observation and on continuous cardiac telemetry and oximetry. They will be on strict bedrest until post-operative Day #1 and they will be ambulated with assistance the morning after the procedure.
- 2 mL blood samples will be drawn at intervals of 4 to 12 hours for up to 48-hours during the post-ablation period. No more than 15 mL total will be drawn. We will use indwelling catheters whenever possible for blood collections. All patients will have indwelling catheters throughout the duration of study, and we do not anticipate needing to perform phlebotomy with a fresh stick during the study. See section 6.12 for full details.

- The research protocol is complete when the participant is discharged from the hospital.

6.3 EP Catheter Placement and Pacing Protocol

The scar and its border zone (defined by peak to peak bipolar voltage of 1 to 2 mV) will have been defined during the clinical procedure (**Figure 5**). Following ablation a 10-pole catheter with 2-8-2 mm interelectrode spacing is positioned in a ventricular area remote from the scar (peak to peak bipolar electrogram voltage > 2 mV) ensuring that electrograms of adequate quality for measurement are present on at least two of the electrode pairs, and that the pacing threshold on one of these pairs is less than 10 mA. The position of this catheter is marked on the 3D-electroanatomic map so that it can be positioned in the same location when the pacing protocol is repeated following administration of the study drug. Pacing threshold is determined, and stimulation is performed at 2-times the threshold. An electrode that has stable capture with pacing is selected for pacing and bipolar signals are recorded from the other electrodes. Pacing is performed at a basic cycle length (CL) of 600 ms (100 beats per minute [bpm]) for 8 beats with the addition of a single extrastimulus followed by a 3 second pause. The initial coupling interval of the extrastimulus is 400 ms. It is then decremented by 10 ms down to loss of capture on two consecutive attempts to define the effective refractory period. The 10-pole catheter is then repositioned to the scar borderzone. The above steps are then repeated at this location. The electrograms from the EP study are exported for offline measurement and analysis. A conduction curve will be plotted to define the conduction time (primary endpoint) and conduction restitution (secondary endpoint).

6.4 Refractoriness

Ventricular Effective Refractory Period (VERP) is defined as the longest stimulus coupling interval which fails to capture the ventricle twice (**Figure 6**). The drive train for ERP testing will be 600 ms.

6.5 Conduction

All measurements of conduction are performed off-line following completion of the procedure and therefore do not prolong case time. They are performed by members of the investigator team who are blinded to drug administration. *Conduction Time* is measured as the time from the: 1) stimulus artifact to the local electrogram on the electrode most distant from the site of pacing that has a consistent reliable electrogram (**Figure 7**). The dominant peak of the bipolar electrogram will be used for measurement of conduction times. If multiple similar amplitude

[figure not shown]

Figure 7: A Conduction Curve for the patient and catheter position in Figure 5. (Inserted panel shows data from the point at the red arrow). At the coupling interval of 290 ms the time from the stimulation artifact to the electrogram at a proximal electrode is 226 ms and is plotted on the conduction curve. The basal conduction time is 140 ms.

beats with the addition of a single extrastimulus followed by a 3 second pause. The initial coupling interval of the extrastimulus is 400 ms. It is then decremented by 10 ms down to loss of capture on two consecutive attempts to define the effective refractory period. The 10-pole catheter is then repositioned to the scar borderzone. The above steps are then repeated at this location. The electrograms from the EP study are exported for offline measurement and analysis. A conduction curve will be plotted to define the conduction time (primary endpoint) and conduction restitution (secondary endpoint).

[figure not shown]

Figure 6: Ventricular effective refractory period (ERP) is displayed for the same patient and catheter position shown in Figure 5. Pacing is from the distal electrode (labeled A in Fig. 5).

signals are present, as may be encountered in or near scar, the latest sharp peak will be used for measurement. Multiple measurements for conduction time will be obtained and are specific to a given location (scar border zone or remote higher voltage site). *Conduction Restitution*⁵⁵: from plots of conduction time versus coupling intervals the following parameters are determined and compared pre-post dantrolene administration: 1) The paced conduction time at basic cycle length; 2) Onset of the paced conduction time increase (the longest coupling interval at which the paced conduction time exceeded that of the basic cycle length by 5 ms and continued to increase); and 3) The maximum paced activation time.

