Conduction Time: is a continuous measurement. To most accurately measure conduction time, it is the mean value of multiple measurements along the horizontal aspect of the conduction curve (**Figure 7**). Conduction time is analyzed separately for the low voltage and higher voltage areas. Multivariable linear regression models will be built. Simple linear regression models will be used to test whether treatment with dantrolene is associated with a statistically significant decrease in mean post-drug conduction time when adjusted for mean pre-drug conduction time. Multivariable linear regression models will include additional adjustment for age, sex, mean bipolar voltage, amiodarone exposure (yes/no), change in beta-agonist exposure, and time from start of drug to post-drug EPS. Mean bipolar voltage will be the mean of the peak electrogram measured on the recording electrode for each of the extrastimuli.

Effective Refractory Period: is a continuous measurement. The ERP is measured at within the low voltage area and higher voltage areas at a drive train of 600 ms. It is measured pre-study drug and post-study drug. Multivariable linear regression models will be built. Separate models will be built for the low and higher voltage areas. Simple linear regression will test whether treatment with dantrolene is associated with a statistically significant increase in mean post-drug ERP when adjusted for mean pre-drug ERP. Multivariable analysis will be conducted using the same methods as described for conduction time.

Secondary Analyses Aim 1: activation time and conduction restitution are additional metrics for conduction. They are analyzed with the same statistical approach as described for conduction time.

Sample Size and Power Aim 1: The primary endpoints are conduction time and ERP. Pre- and post-drug difference in average conduction time and ERP will be compared between the dantrolene and the placebo group. We expect the conduction time to decrease and ERP to increase substantially after drug in the treatment arm, while no change is expected in the placebo arm. With 56 patients treated with dantrolene and 28 placebos, there will be 80% power to detect a $0.6 \times SD$ difference in the average conduction time and the average ERP change between the two study arms.

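### The secondary endpoint of maximum paced activation time has no matched coupling interval, so a longer ERP alone could lower it and be read as faster conduction

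*Combined protocol and SAP*

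**What the plan says.** One pacing scan yields both the ERP and the conduction curve. In Section 6.3, "The initial coupling interval of the extrastimulus is 400 ms", and then "It is then decremented by 10 ms down to loss of capture on two consecutive attempts to define the effective refractory period". Section 6.4 defines the ERP as "the longest stimulus coupling interval which fails to capture the ventricle twice".

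Section 6.5 takes three restitution parameters from the plot of conduction time against coupling interval and states that "the following parameters are determined and compared pre-post dantrolene administration". They are the conduction time at the basic cycle length, the onset of the rise, and "The maximum paced activation time". Onset is "the longest coupling interval at which the paced conduction time exceeded that of the basic cycle length by 5 ms and continued to increase". No coupling interval is named at which the maximum is to be read or matched.

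In Section 10.0 (Secondary Analyses Aim 1), "activation time and conduction restitution are additional metrics for conduction". They are analysed like conduction time: post-drug value on treatment, adjusted for the pre-drug value, with a further model adding age, sex, voltage, amiodarone, change in beta-agonist exposure and time from drug. Neither the ERP nor the shortest captured interval is a covariate. The Aim 1 power paragraph expects the ERP to lengthen on dantrolene and not to change on placebo.

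**The concern.** The curve ends where capture is lost, one step above that run's ERP. If conduction time keeps rising as the interval shortens, the maximum belongs to that last step. A drug that lengthens the ERP then removes the steepest part of the post-drug curve in the dantrolene arm only. The maximum falls although no beat at any interval present in both runs conducts faster.

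Because the plan files this parameter under conduction, the fall would be reported as faster conduction. Aim 1 treats refractoriness and conduction as two effects, so one should not be able to pass for the other. The remote site does not help. The hypothesis predicts effects in low-voltage tissue only, and an ERP rise confined to that tissue would give the maximum the same regional pattern.

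**Working it through.** The plan gives no effect size or power for this parameter, so there is no figure to reproduce. The check is of the mechanism and its possible size.

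**Inputs from the documents.** Scan from 400 ms in 10 ms steps to loss of capture (6.3). Figure 7 text (6.5): basal conduction time 140 ms, and "At the coupling interval of 290 ms the time from the stimulation artifact to the electrogram at a proximal electrode is 226 ms". The rise is 226 − 140 = 86 ms.

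**Assumptions.** A linear rise starting at coupling interval O, with O between 330 and 390 ms, and 290 ms at or near the last captured beat. The documents state none of these.

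**Step 1, end of the curve.** On a 10 ms grid the last captured interval is ERP + 10 ms, separately for each run.

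**Step 2, slope.** b = 86/(O − 290).
- O = 390: 86/100 = 0.86 ms per ms
- O = 350: 86/60 = 1.43
- O = 330: 86/40 = 2.15

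**Step 3, effect of a longer ERP.** Let the ERP rise by E and the curve move right by s, with conduction otherwise unchanged.
- Change in maximum = −b(E − s)
- Change at the shortest interval captured in both runs = +b·s
- Change in onset = s
- Change in onset minus ERP = s − E

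With E = 10 ms and b from 0.86 to 2.15:

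| Curve shift s | Maximum | Matched interval | Onset | Onset − ERP |
|---|---|---|---|---|
| 0 ms | −8.6 to −21.5 ms | 0 | 0 | −10 ms |
| 5 ms | −4.3 to −10.8 ms | +4.3 to +10.8 ms | +5 ms | −5 ms |
| 10 ms | 0 | +8.6 to +21.5 ms | +10 ms | 0 |

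With E = 20 ms and s = 0 the maximum falls by 17.2 to 43.0 ms. For any s from 0 to E the maximum and the matched reading never both fall. If conduction time truly drops by d at every interval and nothing else changes, both fall by d.

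**Step 4, sensitivity to curve shape (s = 0, E = 10 ms).** A straight line from 600 to 290 ms gives 86/310 × 10 = 2.8 ms. An exponential rise, 86 × (1 − e^(−10/τ)) with τ = (O − 290)/ln(86/5), gives 19.6 ms for O = 400 and 43.8 ms for O = 330.

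**Step 5, simulation.** 56 versus 28 patients, no change in conduction, post-drug maximum regressed on arm and pre-drug maximum, two-sided 5%, 3000 runs. Assumed: exponential curve with onset at 350 or 400 ms, ERP test-retest SD 10 ms, measurement noise SD 5 ms.
- No ERP change: 4.9% of trials significant.
- ERP +10 ms on dantrolene, curve unmoved: 97–99% significant, all towards shorter activation time. The matched reading gave 5.9–6.2%.
- ERP +20 ms, curve unmoved: 100% for the maximum, 7–8% for the matched reading.
- Curve shifting right with the ERP: about 5% for the maximum.

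The matched reading was simulated only for an unmoved curve. Its behaviour under a shift comes from Step 3.

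**The case against.** The strongest objection is that the artefact needs a longer ERP with a curve that does not shift equally, and the documents do not favour that over a joint shift. Sections 1.4 and its continuation on dantrolene attribute slowed conduction and shortened refractoriness to the same calcium leak. Under a full shift the maximum is unbiased. This stands, and it limits the point to what can happen.

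A reader might infer that the maximum should be replaced by a matched-interval reading. The arithmetic does not support that: under a full shift the matched reading shows 9 to 22 ms of false slowing per 10 ms. Each reading fails where the other holds, so both are needed.

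A reader might also infer that the plan defines the maximum as the last captured beat. It does not. That follows from the scan rule and the rising curve, and a non-monotone curve could peak earlier. Nor does Section 6.5 say that 290 ms was the last captured interval in Figure 7. The source cited there for restitution may handle this, but it cannot be consulted here.

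A movement in onset is not an error in itself, since onset is defined as a coupling interval. Because the ERP is a primary endpoint, readers will see its change, but nothing in the plan tells them to read the maximum against it. Blinded offline measurement, randomisation and pre-drug adjustment do not remove the problem, because it lies in the definition.

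**Conclusion.** The point holds for one secondary parameter and as a possibility. The maximum is compared before and after drug at intervals that depend on each run's ERP, and the plan expects the ERP to change in one arm only. With an unmoved curve and a linear rise starting at 330 to 390 ms, the false fall is about 9 to 22 ms per 10 ms of ERP. With a full shift it is about zero. These sizes rest on one example point from one patient at a scar border zone, and other assumed shapes give 2.8 to 43.8 ms. The simulated rejection rates show direction and plausibility; they do not predict this trial.

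A reader might infer that the Aim 1 conduction result is itself compromised. It is not. Primary conduction time is averaged over the flat part of the curve, and conduction time at the basic cycle length does not depend on where the scan ends.

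**What to change.** Amend Sections 6.5 and 10.0 before unblinding:

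1. Keep the maximum, and report with it the coupling interval at which it occurred and the ERP change at that site.
2. Add, for the same patient and site, conduction time at the shortest coupling interval captured both pre- and post-drug (or mean delay over the shared intervals), adjusted for the pre-drug value at that interval.
3. Report onset minus ERP beside absolute onset.
4. State in advance that a lower maximum is interpreted as faster conduction only if the matched-interval reading also falls. The matched reading should not stand alone, since it can show false slowing when the whole curve shifts.

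This is preferable to adding post-drug ERP as a covariate, which would condition on an effect of treatment. The curves are already exported and measured offline, so no procedure or data collection changes. The cost is a little more offline analysis and a stricter condition for claiming a conduction effect on this secondary parameter. With a large ERP rise a small residual error remains: 7–8% rejection for the matched reading at 20 ms in the simulation.
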